10.3.1. General Considerations

Descriptive statistics include participant count, mean, median, standard deviation, minimum and maximum for continuous variables and count and percentage for categorical variables. The 95% confidence interval for the mean and the percentiles may also be included, if appropriate. Bleeding related variables will be analyzed and compared between Roctavian Cohort and SoC Cohort using appropriate statistical models including negative binomial model, logistic regression and other appropriate models. Hemostatic treatment variables will similarly be compared.

10.3.2. Approaches to Estimating Comparative Effectiveness

10.3.2.1. Treatment Policy vs. Hypothetical Estimand

Due to the non-randomized, non-interventional nature of this study, two estimands will be considered when estimating the comparative effectiveness of Roctavian to SoC – the treatment policy estimand and the hypothetical estimand. The treatment policy estimand ignores intercurrent events (not applying censoring or any missing data analysis), while the hypothetical estimand may use censoring or missing data analysis methods to derive an estimate incorporating the effect of an intercurrent event like treatment switching. The treatment policy estimand can be overly conservative if switching occurs between the treatment arms in an analysis, while the hypothetical estimand is targeting to adjust for this effect.

Due to the study design, along with the management and administration of Roctavian gene therapy, the treatment policy (similar to intent to treat analysis) is likely to be overly conservative in the setting of this study and the hypothetical estimand is expected to provide more clinically interpretable results. In particular, after the administration of Roctavian, PwSHA will continue their SoC prophylaxis therapy in the initial weeks after infusion and

therefore have a period where bleeding events and hemostatic treatment utilization are not reflective of the treatment effect of only Roctavian. Additionally, participants in the Roctavian Cohort may return to prophylaxis, and due to the non-interventional design PwSHA in the SoC Cohort may switch to Roctavian after the study recruitment window. Further, the hypothetical estimand is consistent with the analyses described in the summary of product characteristics (SmPC) ([BioMarin Intl. Ltd. 2022](#)) and would allow for consistency of interpretation between this study and data described in the SmPC. Although the study sponsor's position is that the hypothetical estimand will provide more clinically interpretable results, the G-BA resolution dated 21, Sept 2023 ([AM-RL 2023b](#)) required the conduct of analyses based on the treatment policy estimand. Therefore, analyses will be conducted and reported utilizing both estimands. Consistency in results for the different estimands and impact on the interpretation of results will be discussed in the interim and final reports.

10.3.2.2. Treatment Policy Estimand

Analyses based on the treatment policy estimand will describe outcomes from index through the end of the follow-up period for both the Roctavian Cohort and SoC Cohort. A participant's time in the analysis will only be censored in the event of a withdrawal, loss to follow-up, death or enrollment in an interventional trial. Follow-up will be censored based on the earliest date after index of withdrawal, loss to follow-up, enrollment into an interventional clinical trial, death (inclusive of date of death), end of reporting/follow-up period in the DHR, or end of study follow-up (eg, index date +3 years). Due to the non-interventional nature of the study and AbD, a participant in the SoC Cohort may subsequently receive Roctavian during follow-up after the recruitment period, if this occurs this participant will be excluded from the analysis. If a participant in the Roctavian Cohort returns to prophylaxis with another hemostatic therapy (eg, exogenous FVIII or emicizumab), this participant will be maintained in the analysis (ie, not excluded from the analysis) as there is a potential continued benefit of the gene therapy after prophylaxis is resumed for effectiveness outcomes and potential long term risk of safety events associated with the gene therapy.

Outcomes for participants in the SoC Cohort who are treated with Roctavian during follow-up after the recruitment period, and are excluded from the analysis, will be described separately. Outcomes will be described for the period these participants were on SoC (index date to date of Roctavian infusion) and treated with Roctavian (date of Roctavian infusion through the end of follow-up).

[Figure 2](#) below illustrates the treatment policy estimand analysis.

Figure 2: Analysis Schema for Treatment Policy Estimand

[figure not shown]

Figure note: Outcomes described from index through the end of the follow-up period for both the Roctavian Cohort and SoC Cohort. A participants’ time in the analysis will only be censored in the event of a withdrawal, loss to follow-up, death or enrollment in an interventional trial (based on earliest date of). Any participant in the SoC Cohort who subsequently receives Roctavian during follow-up after the recruitment period will be excluded from the analysis.

10.3.2.3. Hypothetical Estimand

Analyses based on the hypothetical estimand will describe outcomes during the follow-up period for both the Roctavian Cohort and SoC Cohort, minimizing time periods during which outcomes are confounded by exposure to both gene therapy and SoC prophylaxis. As PwSHA administered Roctavian will remain on prophylaxis for a time following the index date as endogenous FVIII production initiates, the analytical follow-up period for outcomes such as bleeding events and hemostatic therapy utilization for the Roctavian Cohort will begin 5 weeks post-infusion or 3 days after the end of routine FVIII prophylaxis (whichever occurs later), or 27 weeks after end of emicizumab prophylaxis consistent with analyses of the Roctavian clinical trials. The analytical follow-up period of the SoC Cohort will begin on the index date. Participants in the Roctavian Cohort will be censored at the time of resumption of SoC prophylaxis and participants in the SoC Cohort who subsequently receive Roctavian during follow-up after the recruitment period, will be censored on the date of Roctavian infusion. As with the treatment policy estimand, for both cohorts a participant’s time in the analysis will be censored in the event of a withdrawal, loss to follow-up, death or

enrollment in an interventional trial. Follow-up will be censored based the earliest date after index of any of the censoring events described above.

Figure 3 below illustrates the hypothetical estimand analysis.

Figure 3: Analysis Schema for Hypothetical Estimand

[figure not shown]

Figure note: For the Roctavian Cohort, analytical follow-up period for outcomes such as bleeding events and hemostatic therapy utilization will begin on 5 weeks post-infusion or 3 days after the end of routine FVIII prophylaxis (whichever occurs later), or 27 weeks after end of emicizumab prophylaxis consistent with analyses of the Roctavian clinical trials. Participants in the Roctavian Cohort will be censored at the time of resumption of SoC prophylaxis. For the SoC Cohort, analytical follow-up period of the SoC Cohort will begin on the index date. Participants in the SoC Cohort who subsequently receive Roctavian during follow-up after the recruitment period, will be censored on the date of Roctavian infusion.

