7.2.5.2. Use of hemostatic treatments

Endpoints for secondary objectives regarding hemostatic therapy usage will be based on therapeutic usage of exogenous FVIII and emicizumab recorded in the DHR. Key endpoints for comparing use of hemostatic therapy, along with relevant variables collected in the DHR, are described in [Table 7](#). Use of any exogenous FVIII or emicizumab, the number of uses (stratified by prophylaxis vs on-demand/for bleed treatment), amount of exogenous FVIII consumed and number of infusions will be compared between cohorts. Endpoints will be compared based on the total follow-up, as well as specific periods of time starting from index date (eg, during the 2nd or 3rd year of follow-up). Details on the calculation of these outcomes based on the therapeutic usage recorded in the DHR are described further in [Section 10.3](#) and the SAP. Hemostatic therapy usage will be recorded from the index date through the follow-up period for each participant in the AbD.

For the Roctavian Cohort only, the proportion of participants who return to prophylactic hemostatic therapy, along with the time to return to prophylaxis will be described for those in the cohort who ended prophylaxis post Roctavian administration.

Table 7: Hemostatic Treatment During Follow-Up

Variable	Description	Captured in DHR	Time period for Analysis	Entry into DHR	Operational notes including Relevant Data Fields in DHR
Use of hemostatic treatments	Use of any hemostatic treatments	✓	Follow-up	Ongoing	Derived based on therapy usage recorded in the DHR for exogenous FVIII and/or emicizumab.
FVIII Consumption	FVIII consumption during follow-up	✓	Follow-up	Ongoing	Derived based on reported FVIII consumption for each therapeutic use of FVIII, reported for different prophylaxis types (see Table 4) and on-demand use. Will be described based on total FVIII utilized in international units (IUs), as well as IU/KG based on weight data (see Table 3). On demand use of FVIII will be defined as use of FVIII for suspected bleeding, spontaneous bleeding, traumatic, bleeding/bleeding, or intensified on-demand treatment (short-term prophylaxis).
Infusion/ Injection Rate	Number of infusions/ injections during follow-up	✓	Follow-up	Ongoing	Derived based on the therapy usage and frequency of use during individual usage periods recorded in the DHR for any reason and summarized as annualized infusion/injection rate (AIR).

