The proportion of participants utilizing any hemostatic treatments during follow-up will be described but will not be compared as 100% of the SoC Cohort will utilize hemostatic treatments. The relative risk of participants utilizing any hemostatic treatments specifically for bleeds or short-term prophylaxis will be compared consistent with the proportion of participants with zero bleeding events. Also consistent with the analysis of the proportion of participants with zero bleeding, only those participants with follow-up for the full time over which the proportion is calculated will be included in analyses.

The total FVIII per kg administered during follow-up will be compared between the cohorts. Total FVIII per kg for any reason will be compared based on the absolute difference in the mean total FVIII per kg between the Roctavian Cohort and SoC Cohort utilizing a two-sample t-test (two-sided). Similar to the analyses of the proportion of participants with zero bleeding, only those participants with follow-up for the full time over which the proportion is calculated will be included in analyses.

Annualized infusion rates (AIRs) will also be compared between the cohorts. AIRs will be calculated for each participant as the number of infusions or injections divided by the time between the start of follow-up and censoring event for the analysis, annualized to the number of infusions/injections in 1 year. The mean of the individual participant AIRs for each cohort will be calculated and compared. The comparison of AIRs will be based on the absolute difference in the mean AIR between the Roctavian Cohort and SoC Cohort utilizing a two-sample t-test (two-sided).

10.3.7.4. Objective: To compare joint health, quality of life, and pain.

Descriptive statistics will be used to summarize the absolute and change from baseline at the time of assessment for the HJHS. A repeated measurement analysis model will be utilized to describe the overall trend in the HJHS over time. The mean change from baseline to final assessment approximately 3 years after index date will be compared between the Roctavian Cohort and SoC Cohort.

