12.1. Table Shells

All table shells will be populated for the treatment policy estimand. Then the table shells will be adjusted and populated for the hypothetical estimand data analysis, as well as the other sensitivity and subgroup analyses discussed in Section 7.9.5

Table 1 Sample Attrition for Roctavian and SoC Cohorts

Step #	Attrition steps (to be applied sequentially)	Roctavian Cohort				SoC Cohort			
		Excluded		Remaining		Excluded		Remaining	
		N	%	N	%	N	%	N	%
1	Male PwSHA as recorded in the DHR			0	0.00%			0	0.00%
2	≥18 years of age at index	0	0.00%	0	0.00%	0	0.00%	0	0.00%
3	Treated with Roctavian or SoC hemostatic prophylaxis:								
	a) Commercially available Roctavian (Roctavian Cohort)	0	0.00%	0	0.00%				
	b) Prophylactic treatment with FVIII or emicizumab (SoC Cohort)					0	0.00%	0	0.00%
4	Not currently in, or previously participated (in the last 12 months before index), an interventional clinical trial involving an investigational product to treat HA	0	0.00%	0	0.00%	0	0.00%	0	0.00%
5	With no history of inhibitors against FVIII ever (or current) as recorded in the DHR prior to index	0	0.00%	0	0.00%	0	0.00%	0	0.00%
6	With no presence of acute or uncontrolled chronic infections, and/or known significant hepatic fibrosis or cirrhosis at index	0	0.00%	0	0.00%	0	0.00%	0	0.00%
	Final Cohorts			0				0	

Data source: DHR from the start of data collection accompanying the application to approximately 6 months prior to the date of the final report required by the G-BA resolution for AbD

Acronyms: DHR: Deutsches Hämophileregister; SoC: standard of care; PwSHA: people with severe hemophilia A; FVIII: coagulation factor VIII; HA: hemophilia A

Table 2 Baseline and Demographic Characteristics for Roctavian and SoC Cohorts

Measures	Unadjusted						After IPTW					
	Roctavian Cohort		SoC Cohort		p-value (Roctavian vs. SoC)	Std. Diff. (Roctavian vs. SoC)	Roctavian Cohort		SoC Cohort		p-value (Roctavian vs. SoC)	Std. Diff. (Roctavian vs. SoC)
	N=		N=				N=		N=			
	N	(%)	N	(%)			N	(%)	N	(%)		
Age (years)												
Mean	0.00		0.00		0.0000	0.00		0.00		0.0000	0.00	
SD	0.00		0.00			0.00		0.00				
Median	0		0		0.0000	0		0		0.0000		
Q1	0		0			0		0				
Q3	0		0			0		0				
Min	0		0			0		0				
Max	0		0			0		0				
Age categories (years)												
18-40	0	0.0%	0	0.0%	0.0000	0	0.0%	0	0.0%	0.0000	0.00	
41-64	0	0.0%	0	0.0%		0	0.0%	0	0.0%			
≥65	0	0.0%	0	0.0%		0	0.0%	0	0.0%			
18-23	0	0.0%	0	0.0%	0.0000	0	0.0%	0	0.0%	0.0000	0.00	
24-29	0	0.0%	0	0.0%		0	0.0%	0	0.0%			

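### Under the hypothetical estimand, routine prophylactic use in the Roctavian Cohort is zero by the window rule, so its comparison with SoC carries no information; total FVIII/kg and AIR are tilted but not fixed

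*Protocol*

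**What the plan says.** Protocol 10.3.2.3 applies the hypothetical window to consumption as well as to bleeds; it governs "the analytical follow-up period for outcomes such as bleeding events and hemostatic therapy utilization for the Roctavian Cohort".

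- **Opening, Roctavian Cohort:** "5 weeks post-infusion or 3 days after the end of routine FVIII prophylaxis (whichever occurs later), or 27 weeks after end of emicizumab prophylaxis".
- **Closing, Roctavian Cohort:** "Participants in the Roctavian Cohort will be censored at the time of resumption of SoC prophylaxis".
- **SoC Cohort:** "The analytical follow-up period of the SoC Cohort will begin on the index date".

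SAP 7.2.3 repeats these rules.

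Prophylactic treatment is one of two endpoints listed in Protocol Table 1 under the objective of comparing hemostatic medication use. Protocol 7.2.5.2 says that "the number of uses (stratified by prophylaxis vs on-demand/for bleed treatment), amount of exogenous FVIII consumed and number of infusions will be compared between cohorts". Protocol 10.3.7.3 adds "Total FVIII per kg for any reason will be compared based on the absolute difference in the mean total FVIII per kg", by two-sample t-test and restricted to participants with complete follow-up for the period. It also adds a t-test on AIR, where each participant's rate runs from the start of follow-up to the censoring event of the analysis in question.

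Shell Table 9 in SAP 12.1 has prophylactic FVIII and emicizumab rows, each with a Roctavian versus SoC p-value column. The shells are filled first for the treatment policy estimand. "Then the table shells will be adjusted and populated for the hypothetical estimand data analysis".

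**The concern.** For bleeding, a return to prophylaxis can reasonably be handled as an intercurrent event. For consumption it is part of the outcome. Selecting Roctavian person-time on the absence of prophylaxis, and then comparing prophylaxis use in that time with SoC, measures the selection rule.

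A secondary objective of a benefit-assessment study could therefore carry a p-value for a contrast whose Roctavian side is known beforehand. The plan also describes this estimand as the more clinically interpretable of the two (Protocol 10.3.2.1), so readers are steered towards it.

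**Working it through.** The plan gives no figure for this objective. Its only computed figure, the total sample size of 397, belongs to the primary bleeding-rate comparison and does not enter here. The check is therefore of the rules, followed by an illustration of size.

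**Step 1: what the window can contain.**

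- It opens after routine FVIII or emicizumab prophylaxis has ended, under Protocol 10.3.2.3 as worded.
- It closes when prophylaxis resumes.
- A participant who never stops prophylaxis never enters it.
- Short-term prophylaxis does not put anything back into the prophylactic total, because Protocol Table 7 classes it as on-demand use.
- Resumption is taken from a physician's report in the register (Protocol Table 7). Prophylaxis entered without that report could remain in the window. That is a recording gap, not a designed contribution.

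Routine prophylactic use in the Roctavian window is therefore 0 IU/kg and 0 mg/kg at any resumption rate from 0% to 100%.

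**Step 2: which comparisons are affected, and how far.**

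| Quantity | Roctavian side under this estimand |
|---|---|
| Prophylactic FVIII or emicizumab | Zero by construction |
| AIR | Prophylactic infusions removed; other use remains |
| Total FVIII/kg, any reason | Prophylactic part removed; the complete-follow-up condition also drops everyone censored at resumption |
| On-demand use | Not fixed by the rule |

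**Step 3: does anything exempt prophylactic use?** No statement was found. Protocol 10.3.7.3 declines to compare the proportion with any hemostatic use, because the SoC result is 100% by definition. It does not apply the same reasoning where the Roctavian result is zero by definition.

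**Step 4: size, by illustration.** The documents give no resumption rate, so these inputs are assumptions: 3 years of follow-up, 5 weeks of continued prophylaxis after infusion, and resumption times uniform over the remaining time. SoC participants are taken as on FVIII prophylaxis throughout, at the same rate as Roctavian participants when on prophylaxis. The range of 20–40 IU/kg at 2–3 day intervals, which SAP Table 4 lists for several products, gives 20 × 365.25/3 = 2,435 to 40 × 365.25/2 = 7,305 IU/kg per year. The rate cancels in the ratio.

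- Bridging: 35/365.25 = 0.096 years, and 0.096/3 = 3.2% of follow-up.
- Resumption: mean time on prophylaxis among those who resume is (3 − 0.096)/2 = 1.452 years, and 1.452/3 = 48.4% of follow-up.
- Roctavian use as a share of SoC = 3.2% + 48.4% × proportion resuming.

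| Proportion resuming | Index to end of follow-up | Hypothetical window |
|---|---|---|
| 0% | 3% | 0% |
| 10% | 8% | 0% |
| 30% | 18% | 0% |
| 50% | 27% | 0% |
| 80% | 42% | 0% |
| 100% | 52% | 0% |

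A second set of assumptions behaves the same way. Take 30 IU/kg 2.5 times weekly, so 30 × 2.5 × 52 = 3,900 IU/kg per year and 11,700 over 3 years; 8 weeks of bridging (8/52 × 3,900 = 600); and 1.5 years on prophylaxis after resumption.

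- 20% resuming: 600 + 0.20 × 1.5 × 3,900 = 1,770 IU/kg, and 1,770/11,700 = 15%.
- 40% resuming: 600 + 0.40 × 1.5 × 3,900 = 2,940 IU/kg, and 2,940/11,700 = 25%.

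The hypothetical window gives 0% in both.

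**The case against.** The strongest defence is that the informative analysis is already planned. Both estimands are reported, and the treatment policy version runs from index, keeps those who return to prophylaxis (Protocol 10.3.2.2) and fills the shells first. Resumption has its own objective, covering the proportion returning, time to return, and use at 3 and 6 months afterwards (Protocol 10.3.7.6; SAP 7.9.4.6). The reports must also discuss consistency between the estimands. All of this stands and limits the harm. It does not give the hypothetical comparison of prophylactic use any content.

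The amount of formal testing is also arguable. Protocol 10.3.7.3 names tests on total FVIII/kg, AIR and use for bleeds or short-term prophylaxis, but none on prophylactic amount alone. SAP 7.9.4.3 says that prophylactic and on-demand use are described. Secondary p-values are nominal (SAP 7.9), and the shells are to be adjusted for this estimand. Against that, Protocol Table 1 and 7.2.5.2 call for a comparison, and shell Table 9 provides the p-value.

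The window itself is not stated consistently. SAP 7.3.3.2 puts the start relative to a time before prophylaxis ends, where Protocol 10.3.2.3 and SAP 7.2.3 say after. SAP 7.4.3 collects all outcomes from index in both cohorts, and SAP 7.9.4.3 borrows the follow-up approach of SAP 7.9.3, which starts at index. Read literally, these would let bridging prophylaxis in. They create no stated exemption, and SAP 7.3.3.2 keeps censoring at a switch back to SoC.

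Finally, the illustration rests on assumed inputs, and a large reduction appears in most rows either way. Emicizumab users in the SoC Cohort contribute no prophylactic FVIII, so the absolute IU/kg figures would be lower in the pooled cohort.

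**Conclusion.** The point holds for routine prophylactic use. Under the wording of Protocol 10.3.2.3 and SAP 7.2.3, the Roctavian value is zero apart from recording gaps, and the contrast with SoC says nothing about the treatment effect. In the first illustration the estimand hides actual use of about 3% to 52% of the SoC level; that range depends on the stated assumptions, while the zero does not.

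A reader might infer that the whole hemostatic-use objective is decided in advance. The documents do not support that. Total FVIII/kg and AIR retain on-demand, surgical and short-term prophylaxis use, so they are tilted in Roctavian's favour without being fixed. Nor would a return to prophylaxis go unreported, since the treatment policy analysis and the resumption objective both show it.

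This is a circular secondary comparison that should be removed. It does not threaten the study's main conclusion.

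**What to change.** 1. In Protocol 10.3.2.3 and 10.3.7.3 and SAP 7.2.3 and 7.9.4.3, state that between-cohort comparisons of prophylactic use, total FVIII/kg and AIR are made only over the treatment policy window, from index to end of follow-up, with bridging and resumed prophylaxis counted.
2. Limit the hypothetical estimand in this objective to on-demand use. Alternatively, show its prophylactic, total and AIR rows in shell Table 9 as descriptive, without p-values, and with a note that prophylaxis is excluded by definition.
3. Reconcile the analysis-window start in SAP 7.3.3.2, 7.4.3 and 7.9.3 with Protocol 10.3.2.3 and SAP 7.2.3.

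The cost is wording and some table rows; no new data are needed. The reported reduction in consumption will look less favourable to Roctavian.

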7.1. Overview of Data Collection

All data for this study will be collected and stored in the DHR. Study site personnel are responsible for participant data collection and data entry into the DHR.

[Table 2](#) specifies the data collection elements of interest to be collected for this study as they occur in accordance with the standard clinical care consistent with the AbD.

Data entered into the DHR must be documented in each participants medical records (source documents). Baseline data will be derived based on information entered into the DHR prior to index date. Further detail on data fields within the DHR that will be used for both baseline and follow-up data are described further in Sections [7.2.3](#), [7.2.4](#), and [7.2.5](#). All data fields in Sections [7.2.3](#), [7.2.4](#), and [7.2.5](#) are mandatory to complete for individuals who consents to participate in this data collection. Data fields in the DHR (described in Sections [7.2.3](#), [7.2.4](#), and [7.2.5](#)) are either mandatory to be entered into the registry per DHR practices or will be monitored (see Section [7.1.2](#)) to ensure completeness of data for analyses.

Table 2: Data Elements of Interest

Variables	Baseline Data (prior to index)	At index	Data entered as observed after index	End of Follow-up (3 years post index)
Demographic and Disease Information				
Documentation of hemophilia disease and severity	X			
Demographics, including height and weight	X	X		
Inhibitor Status	X		X	X
Clinical Trial Participation	X ^a		X	
Comorbidities of interest	X			
Bleeding Events, Hemostatic Treatment Usage, & Gene Therapy Information				
Bleeding Events	X ^a		X	X
SoC Hemostatic Treatment Usage	X		X	X
Gene Therapy Information		X ^b		
AAV Serostatus Testing Information	X	X		
Use of immunosuppression for gene therapy		X ^b	X ^b	
FVIII Activity Levels			X ^b	
Clinical Outcome Assessments				
Haemo-QoL-A questionnaire	During baseline or Index ^c	During baseline or Index ^c	Bi-Annually ^d	At end of study period or participant discontinuation ^f
Hemophilia Joint Health Score (HJHS)	During baseline or Index ^c	During baseline or Index ^c	Annually ^e	At end of study period or participant discontinuation ^f
BPI-SF	During baseline or Index ^c	During baseline or Index ^c	Bi-Annually ^d	At end of study period or participant discontinuation ^f

Variables	Baseline Data (prior to index)	At index	Data entered as observed after index	End of Follow-up (3 years post index)
Safety Information				

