7.3.3.2. Censoring and Follow-up Criteria due to Hypothetical Estimand

Analytical Considerations

For the analysis under the hypothetical estimand, the following additional censoring criteria will be applied:

- Treatment switching from SoC to Roctavian (or vice versa) anytime during the study period
- Analytical follow-up time after Roctavian administration before 5 weeks post-infusion or 3 days before the end of routine FVIII prophylaxis (whichever occurs later), or 27 weeks before end of emicizumab prophylaxis (for outcomes such as bleeding events and hemostatic therapy utilization)

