On-demand hemostatic treatments	Yes (calculated)	
 Occasion Preparation/medicinal product Weight Consumption/delivery Treatment date Start of reporting period 	
 Amount of on-demand FVIII utilized per participant over time (IU or mg), as well as per participant per kg over time (IU/kg) for FVIII products and mg/kg for emicizumab for a bleeding event (occasion = "suspected bleeding", "spontaneous bleeding", "traumatic bleeding/bleeding", or "intensified on-demand treatment (=short-term prophylaxis)") Amount of on-demand FVIII utilized per participant over time (IU or mg), as well as per participant per kg over time (IU/kg) for FVIII products and mg/kg for emicizumab for short-term prophylaxis (occasion = "intensified on-demand treatment (=short-term prophylaxis)") 	
 ≥1 year ≥2 years ≥3 years All available follow-up

Variable	Captured in DHR	DHR data field name(s)	Operational definition and calculation of outcome measures	Timepoints for data collection
		
 End of reporting period 	
 Each participant's average weight over the reporting period will be used when calculating IU/kg 	
FVIII Infusion/injection rate	Yes (calculated)	
 Preparation/ medicinal product Frequency Start of reporting period End of reporting period 	
 Number of infusions/injections from the index date through the follow-up period Derived based on the therapy usage and frequency of use during individual usage periods recorded in the DHR for any reason and summarized as AIR 	
 ≥1 year ≥2 years ≥3 years All available follow-up
Time to resumption of prophylactic treatment	Yes	
 Did the patient have to return for prophylaxis? Date of return to prophylaxis Date of gene therapy 	
 Roctavian Cohort only Derived based on the recording of whether the patient had to return for prophylaxis and if yes, the time (days) between the date of gene therapy and date of return to prophylaxis 	All available follow-up
Clinical Outcome Assessments				

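### Censoring Roctavian participants at return to prophylaxis, with no adjustment or sensitivity analysis, probably favours Roctavian and measures bleeding while off prophylaxis, not bleeding had prophylaxis never been resumed

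*Protocol*

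**What the plan says.** Protocol section 10.3.2.1 sets up two estimands. It presents the treatment policy estimand as conservative when participants switch, and says that "the hypothetical estimand is targeting to adjust for this effect". In general terms it adds that "the hypothetical estimand may use censoring or missing data analysis methods to derive an estimate".

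Section 10.3.2.3 then fixes the method: "Participants in the Roctavian Cohort will be censored at the time of resumption of SoC prophylaxis". The SAP bound with the protocol repeats this in section 7.2.3, and section 7.3.3.2 lists as a censoring event "Treatment switching from SoC to Roctavian (or vice versa) anytime during the study period". In SAP Table 5 (section 7.4.3), time to resumption is "Derived based on the recording of whether the patient had to return for prophylaxis".

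Under the treatment policy estimand (section 10.3.2.2), when a Roctavian participant returns to prophylaxis, "this participant will be maintained in the analysis (ie, not excluded from the analysis". Section 10.3.2.1 promises that "analyses will be conducted and reported utilizing both estimands", and states the sponsor's view that the hypothetical one is easier to interpret clinically.

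For annual-increment ABRs (protocol 10.3.6, SAP 7.9.3) only participants with complete follow-up for the period are included. Protocol 10.3.7.2 applies the same restriction to the zero-bleed proportions. Section 10.3.6 itself expects censoring to shrink the final annual-increment samples.

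**The concern.** A hypothetical estimand for resumption asks how much a man would have bled over three years had he not gone back to prophylaxis. Stopping his clock at resumption answers that only if resumption is unrelated to the bleeding he would otherwise have had. A field asking whether the patient had to return suggests the opposite: men return because the effect has faded. Their unobserved off-prophylaxis time would then be worse than that of the men who stay in, and leaving it out lowers the Roctavian ABR.

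Nothing in the plan deals with this. The sensitivity analyses in SAP 7.9.5 cover switching on the SoC side and traumatic bleeds. The multiple imputation in SAP 7.9.5.1 is for propensity-score covariates. The bias assessment in SAP 7.10 concerns unmeasured confounding.

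At stake is what the sponsor's preferred analysis can show. If waning of effect largely drops out of the estimate, a product that fades in some men can look nearly as good as one that lasts.

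**Working it through.** **The plan's own figure.** Protocol 10.1 and SAP 7.6 use rates of 3 (SoC) and 0.85 (Roctavian), null ratio 0.5, θ = 0.2, φ = 1.5, one year of exposure, one-sided α = 0.025 and 80% power.

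- V0 = (1 + 0.5×0.2)² / [0.5×0.2×(3 + 0.2×0.85)] + 1.2×1.5/0.2 = 12.82
- V1 = 1/3 + 1/(0.2×0.85) + 9 = 15.22
- N1 = (1.960√12.82 + 0.842√15.22)² / (ln 0.5 − ln 0.2833)² = 328.8

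This gives 329 + 66 = 395 against the stated 397. The planning inputs are therefore understood, and the planned ratio is 0.85/3 = 0.283.

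**Assumed inputs (none is in the documents).** A share f of 10-30% loses response, at times spread evenly over the three years. The rate after loss is r = 3, 5 or 10 per year. The lag from loss to resumption averages up to two months.

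**Ratio had prophylaxis not been resumed.** On average half of the three years lies after loss, so RR = [0.85 + (f/2)(r − 0.85)]/3.

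| f | r = 3 | r = 5 | r = 10 |
|---|---|---|---|
| 10% | 0.32 | 0.35 | 0.44 |
| 20% | 0.36 | 0.42 | 0.59 |
| 30% | 0.39 | 0.49 | 0.74 |

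Setting RR = 0.5 gives the rate needed to reach the margin, r = 0.85 + 1.30/f: 13.9 per year at 10%, 7.4 at 20% and 5.2 at 30%.

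**Ratio when censored at resumption.** With no lag it is 0.283 whatever f is. With an exponential lag averaging two months, pooled events over person-time gives 0.29-0.34 across the table, and the mean of individual ABRs (protocol 10.3.6) gives 0.29-0.41. The negative binomial model with a follow-up offset (SAP 7.9.3) gives each man weight 1/(1 + φλt), for follow-up time t and event rate λ. That should place its estimate between the two.

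**One case by hand.** Let f = 30%, resumption at 1.5 years, a three-month lag and r = 6. A resumer has 0.85×1.25 + 6×0.25 = 2.56 bleeds before censoring.

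- Censored, pooled: (0.7×2.55 + 0.3×2.56)/(0.7×3 + 0.3×1.5)/3 = 0.33
- Censored, mean of individual ABRs: (0.7×0.85 + 0.3×2.56/1.5)/3 = 0.37
- Not resumed: [0.7×0.85 + 0.3×(0.85×1.25 + 6×1.75)/3]/3 = 0.58
- Treatment policy, if resumed men bleed at 3 per year: [0.7×0.85 + 0.3×(2.56 + 3×1.5)/3]/3 = 0.43

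With a six-month lag, the two censored values become 0.38 and 0.46, against 0.63 without resumption.

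**Annual increments.** A man censored at 1.5 years does not have two years of analytical follow-up. He therefore leaves the two- and three-year ABR and zero-bleed comparisons, and his bleeds between loss and resumption, which the full-follow-up analysis counts, go with him.

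**The case against.** The strongest reply is that the treatment policy analysis is mandatory, keeps resumers and is reported alongside. SAP Annex 12.1 fills the table shells for it first, and resumption is described as a separate secondary objective (protocol 10.3.7.6). All of that stands, so the censored figure will not appear alone. It does not make the censored figure an estimate of bleeding without resumption. The treatment policy result answers a different question, because resumers bleed there under prophylaxis. The resumption summary also does not put the censored person-time beside each ABR.

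Four stronger readings are tempting, and the documents do not support them.

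- *That censoring turns a ratio above 0.5 into about 0.3.* This needs assumed inputs at the severe end. Most of the grid stays below 0.5, and protocol 10.3.2.2 itself allows for continuing benefit after resumption.
- *That only responder time is counted.* In the full-follow-up analysis, bleeds between loss and resumption count, and the mean of individual ABRs gives short, bleed-heavy follow-up full weight. The description comes close to true only in the two- and three-year increments.
- *That SoC has no counterpart.* SoC participants who later receive Roctavian are also censored, at infusion.
- *That the trigger for resumption is documented.* Table 7 records a physician's report of return and the SAP field asks whether the patient had to return. The link to loss of effect is an inference, though a reasonable one.

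**Conclusion.** The point holds as a fault of estimation and labelling, and it should be fixed. Plain censoring at resumption is fixed in both texts with nothing to account for its likely dependence on the outcome. The probable direction favours Roctavian, and the quantity estimated is bleeding while off prophylaxis.

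On the planning rates, with the assumed 10-30% loss of response and 3-10 bleeds per year afterwards, the gap is between about 0.32-0.74 without resumption and about 0.28-0.41 when censored after a lag averaging up to two months. At the mild end the difference is a few hundredths. Only 20-30% loss combined with 10 bleeds per year passes 0.5 in the table.

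A reader might infer that a decision would flip. That does not follow: with resumed men bleeding at 3 per year, the treatment policy ratio over the same grid is about 0.32-0.43. In addition, the test against 0.5 is specified only in SAP 7.9.3, while protocol 10.1 says that the actual null hypotheses are not shifted.

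**What to change.** - Label the plain-censored analysis as bleeding while off prophylaxis, or state the hypothetical scenario and use a method that targets it.
- Beside every hypothetical-estimand result, give the number of Roctavian participants and the person-time censored at resumption.
- Prespecify a sensitivity analysis for informative censoring, before the SAP is finalised ahead of the first data cut. Multiple imputation of off-prophylaxis bleeding after resumption, over a stated range of rates, is the practical choice. Use censoring weights only if they prove stable.
- In the annual-increment and zero-bleed analyses, keep the bleeds that resumers had before resumption.
- State that the treatment policy analysis carries any conclusion against the 0.5 margin.

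The cost is wording in both texts, one or two extra models and wider intervals. Weighting is the uncertain part. With about 70 men, 10-30% is only 7-21 resumptions, and if nearly all men who lose response resume quickly, few remain to carry weight. Table 2 lists "FVIII Activity Levels" after index for the Roctavian Cohort but sets no schedule, so the data for a weighting model may be thin.
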